Since the advent of NIRF, imaging technology has improved, with increasing sensitivity and improved intraoperative displays. Whether these improvements have resulted in increased sensitivity and utility has not yet been demonstrated, nor has the possibility of whether improved technology has decreased either the dose required for adequate visualization or the time interval prior to optimal visualization.

5. Specific Aim:

To compare the efficacy and utility of a low dose ICG (0.05 mg) protocol with a previously published dose (2.5 mg) in imaging the extrahepatic biliary tract.

6. Research Plan:

Current standard of care for this service is to administer 2.5 mg of ICG preoperatively to patients before surgical bile duct visualization. If there is any further need for anatomic information, then a combination of ultrasound and X-ray cholangiography is used. For this study, adult patients scheduled to undergo a laparoscopic hepatic or biliary operation will be randomized to two groups 1) low dose (0.05 mg) or 2) standard dose (2.5 mg) of ICG preoperatively on the day of surgery. Patients with a history of adverse reactions or known allergy to ICG, iodine, or iodine dyes will be excluded. Pregnant and/or lactating patients will also be excluded. Participants will receive a baseline assessment. Demographic information, including age, gender, ethnicity or race, body mass index, American Society of Anesthesiologists class, preoperative diagnosis, liver function, and complete medical history, will be collected. Case difficulty will be graded by the primary surgeon based on standardized criteria (<https://pubmed.ncbi.nlm.nih.gov/29956029/>). The PINPOINT Endoscopic Fluorescence Imaging System (Stryker Corporation, Kalamazoo, Michigan) will be used. This device enables the surgeon to simultaneously see real-time, high-definition visible-range and NIR fluorescence videos and to superimpose them. It is currently approved by the FDA for intraoperative near-infrared fluorescence imaging. Essentially, it is a standard laparoscopic device with an added excitation laser at 805 nm and a filter set to allow for visualization of ICG fluorescence. The visualization of the biliary tree will be recorded.

Low dose or standard dose ICG will be administered by the anesthesiologist as guided by the study coordinator at the beginning of the case. The operating surgeon will be blinded to the dose given. At two points during the operation (1- prior to the

[figure not shown]

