Figure 1. Representative examples of intraoperative images of biliary tract. GB, gallbladder; L, liver; CHD, common hepatic duct; Cys, cystic duct. (Zarrinpar et al, *Surgical Innovation* 2016)

dissection of the biliary tract and 2- upon completion of the dissection and establishment of the critical view of safety), a *qualitative assessment* will be made by the primary surgeon based on the quality of the intraoperative visualization of the extrahepatic biliary tree (being able to identify and distinguish the common bile duct, the common hepatic duct, and the cystic duct from the surrounding structures and from each other) on a scale of 1 to 5 (1 = no improvement/identification not confirmed; 2 = marginally improved; 3 = sufficiently improved; 4 = well improved; 5 = greatly improved/exceeds expectations). The recorded visualization will also be assessed by a blinded independent surgeon who will use the same scale. A quantitative assessment will also be performed on the recorded visualization using ImageJ (US National Institutes of Health, Bethesda, MD; <http://imagej.nih.gov/ij/>) by dividing the fluorescence intensity signal of the common bile duct by that of the surrounding fat or liver. These quantitative measurements will allow an independent measure of duct visualization. Both quantitative and qualitative scores will be compared to determine whether there are significant differences between the doses. A total of thirty patients (15 in each arm) will be required for more than a 90% power to detect a difference in the duct-to-liver ratio of 0.2 between the two groups, given an alpha of 0.05 and a standard deviation of 0.15. These estimates are based on our previously published results. (5)

Patients who are not able to provide informed consent and have a history of sensitivity or allergy to shellfish, ICG, or iodine will be excluded from the study.

Randomization: Identical envelopes will be made with a card marked either standard or low dose to be chosen in blocks of four. At the time of enrollment, an envelope will be selected at random from a box and the subject will be assigned to the corresponding arm. This envelope will then be discarded to allow for equal numbers in each group.

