10.2 Site Monitoring

10.3 Principal Investigator Responsibilities

As part of the responsibilities assumed by conducting this study, the Principal Investigator (PI) agrees to maintain and have available for monitoring adequate case records (accurate source documents and CRFs) for the subjects treated under this protocol.

The PI will be primarily responsible for monitoring of adverse events, protocol violations, and other immediate protocol issues. The study coordinator will collect information on subjects enrolled through the use of electronic or paper adverse event (AE) forms, CRFs, and Informed Consent forms.

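### Fixed blocks of four let anyone who tracks earlier doses foresee about 31% of allocations, and nothing in the plan separates that knowledge from enrollment

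*Protocol*

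**What the plan says.** The randomization paragraph of protocol section 6 (Research Plan) reads: "Identical envelopes will be made with a card marked either standard or low dose to be chosen in blocks of four". It continues: "At the time of enrollment, an envelope will be selected at random from a box and the subject will be assigned to the corresponding arm". Draws are without replacement: "This envelope will then be discarded to allow for equal numbers in each group". The block size is therefore fixed and printed in the protocol. The paragraph does not give the make-up of a block, who draws, how envelopes are sealed, or whether blocks run within center.

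The same section has the dose "administered by the anesthesiologist as guided by the study coordinator", while the operating surgeon and the independent reader of the recordings are to be blinded. Section 10.3 adds, of the same role: "The study coordinator will collect information on subjects enrolled", by way of adverse event forms, CRFs and consent forms. Section 2 lists one study coordinator.

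On size, section 6 states: "A total of thirty patients (15 in each arm) will be required". The SAP gives 26 (13 per arm) and says the study was powered so that each center could accrue enough subjects on its own. Neither document gives the number of centers.

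**The concern.** A fixed block drawn without replacement gives itself away. Once two cards of one kind have been used, the rest of the block is known. Opaque, sealed envelopes do not prevent this, because the information comes from the block size and the history. Both are available to someone who guides each dose and can read the protocol.

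If that person can influence which patient is enrolled next, or when, patients can be steered between arms, knowingly or not. The population is mixed: any adult having a laparoscopic hepatic or biliary operation. BMI and liver function are recorded, and section 4 says ICG is cleared only by the liver, so patient features could plausibly affect the duct-to-liver ratio. Section 7 warns that the low dose may visualize less well, which is a conceivable motive for holding back a hard case. With 13 to 15 per arm a few such patients could matter, and the SAP's tests (Mann-Whitney, 2-way ANOVA) name no baseline adjustment.

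**Working it through.** **The plan's own figure.** Inputs from section 6: difference 0.2, and "given an alpha of 0.05 and a standard deviation of 0.15". The standardized difference is 0.2/0.15 = 1.33. A two-sided t-test (sidedness is assumed) needs 12.86, so 13 per arm, for 90% power, which matches the SAP. At 15 per arm power is 94.1%, consistent with the protocol's claim of more than 90%. The sample size reproduces.

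**Predictability.** Assumptions: two low and two standard cards per block, one sequence, and an observer who knows the block size and all earlier doses. There are 6 equally likely orders.

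| Position in block | Chance the arm is certain | Chance the best guess is right |
|---|---|---|
| 1 | 0 | 1/2 |
| 2 | 0 | 2/3 |
| 3 | 1/3 | 1/3 × 1 + 2/3 × 1/2 = 2/3 |
| 4 | 1 | 1 |
| Sum per block | 4/3 | 17/6 |

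- N = 30 is 7 blocks + 2. Certain: 7 × 4/3 = 9.33, or 31.1%. Best guess right: 7 × 17/6 + 1/2 + 2/3 = 21.0, or 70%, against 15 by chance.
- N = 26 is 6 blocks + 2. Certain: 6 × 4/3 = 8.0, or 30.8%. Best guess right: 6 × 17/6 + 1/2 + 2/3 = 18.17, or 69.9%.
- In complete blocks only, the rates are (4/3)/4 = 33% and (17/6)/4 = 71%.

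**Balance.** Both totals leave two patients in an unfinished block. The first two cards of a block match with probability 2/6 = 1/3.

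- At 30: 15:15 with probability 2/3, otherwise 16:14. Power is 94.1% against 94.0%.
- At 26: 13:13 with probability 2/3, otherwise 14:12. Power is 90.3% against 90.2%.
- If two centers each ran their own blocks (an assumption) and 30 were the combined total, 15:15 would have probability 1/2 to 2/3, and the split would never be worse than 16:14.

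**Alternative: one shuffled list of n + n.** Expected certain allocations are 2n/(n+1). Expected correct best guesses are n − 1/2 + 2^(2n) / (2 × C(2n, n)).

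- n = 15: certain 30/16 = 1.875 of 30 (6.3%); best guess 59.9%.
- n = 13: certain 26/14 = 1.857 of 26 (7.1%); best guess 60.5%.
- Price of this option: if a center stops at 20 of 30, the arms are 10:10 with probability C(15,10)² / C(30,20) = 3003² / 30,045,015 = 30%. Five complete blocks of four would give 10:10 for certain.

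**The case against.** **The link to enrollment is inferred.** A reader might infer that the coordinator recruits patients and can time them. The documents do not say so. Section 10.3 concerns gathering information on people already enrolled, and handling consent forms is not the same as obtaining consent. No section says who draws the envelope. This stands, and it limits the point to a risk. The remaining weakness is that nothing keeps the role that knows past doses away from enrollment.

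**One observer of one sequence is assumed.** The title says multicenter, and the documents do not say whether one coordinator sees every allocation. If blocks ran across centers and each coordinator saw only part of the sequence, predictability would be lower. This also stands.

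**The box might hold all the cards.** A random draw from a box, with used envelopes discarded, could describe one set of 15+15, which would already give equal arms and about 6% certain allocations. That reading contradicts the stated blocks of four, so it shows that the text needs clarifying without removing the problem.

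**Equal numbers.** A reader might infer that the scheme fails to deliver 15 per arm. It does not fail: 15:15 is the most likely outcome, and the stated aim is to allow for equality. Only the guarantee is missing.

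**Bias is not quantified, and the assessors are blinded.** Both are true. Blinding protects the scoring but does not protect the choice of who enters each arm. The calculation measures how much can be foreseen, not any shift in the result.

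**Conclusion.** The point holds as a correctable weakness in allocation concealment. Given 2+2 blocks, one observed sequence and knowledge of earlier doses, about 31% of allocations (9.3 of 30) are certain in advance, and a best guess is right about 70% of the time. The documents do not show that anyone would be in a position to use this. They also contain no safeguard against it. A conclusion that selection bias occurred, or that a particular role steered patients, would go beyond the text.

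The balance point is secondary. Equal arms have probability 2/3 in a single sequence, the worst case is 16:14 (or 14:12), and the power cost is about 0.1 percentage point.

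**What to change.** Within each center, replace the fixed blocks of four by one of two schemes:

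- **One pre-shuffled list** with exactly the planned number per arm. Certain allocations fall to about 6% (7% at 13+13), and equal arms are guaranteed if the center reaches its target.
- **Concealed, varying block sizes** that sum to the planned total. These limit imbalance if a center stops early but leave somewhat more predictability than the single list.

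Under either scheme, have the list prepared by someone who does not enroll patients, keep block details out of the site protocol, and state who enrolls, who draws, and how envelopes are sealed.

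The cost is a few sentences in the randomization paragraph and a re-shuffled set of cards. The single list's downside is unequal arms if a center stops short (10:10 at 20 of 30 only 30% of the time). Section 10.4 plans no stopping rule, but that does not protect against slow accrual, so the choice should depend on how sure each center is of reaching its number.

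The SAP is written in the past tense. If enrollment is complete, report how allocation was actually done and who held which information, and show BMI and liver function by arm.

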10.1 Data Integrity and Safety Committee

This protocol summary will include a minimum of the following:

- The UF IRB assigned protocol number, protocol title, PI name, data coordinator name or primary study coordinator, regulatory coordinator name, and statistician
- Date of initial UF IRB approval, date of most recent consent UF IRB approval/revision, date of UF IRB expiration, study status, and phase of the study, study target accrual and study actual accrual.
- Protocol objectives with supporting data and list of number of study participants who have met each objective.
 - Intraoperative measures
- Summary of toxicities and protocol deviations.
- Summary of any recent literature which may affect the safety or ethics of the trial.

10.2 Site Monitoring

10.3 Principal Investigator Responsibilities

As part of the responsibilities assumed by conducting this study, the Principal Investigator (PI) agrees to maintain and have available for monitoring adequate case records (accurate source documents and CRFs) for the subjects treated under this protocol.

The PI will be primarily responsible for monitoring of adverse events, protocol violations, and other immediate protocol issues. The study coordinator will collect information on subjects enrolled through the use of electronic or paper adverse event (AE) forms, CRFs, and Informed Consent forms.

10.4 Interim Analyses & Stopping Rules

As a phase II feasibility study, our goal is to establish clinical and operative expectations around the use of low-dose IV ICG. Given the standard use of standard dose IV ICG, we are not concerned about safety, so a phase I study or safety run-in of low dose ICG is not felt to be needed. However, we will monitor and record any AEs related to the IV ICG administration in both arms of the study.

Given the published safety data on intraoperative use of ICG, we do not anticipate any safety issues between the standard and low dose ICG, but will monitor AEs related to ICG administration in real time. A pre-planned stopping rule for safety is not needed.

Given the pilot and feasibility aspects of this study such that a primary efficacy difference is not being targeted along with the relatively small numbers of patients and short enrollment period, a stopping rule for efficacy is not appropriate.

11. References

Low vs Standard Dose Indocyanine Green in the Identification of Biliary Anatomy Using Near-Infrared Fluorescence Imaging: A Multicenter Randomized Controlled Trial

NCT04942665

9/1/2022

Mann-Whitney tests were conducted for the quantitative and qualitative assessments to identify any significant differences between the 2 doses of ICG. A 2-way ANOVA was also conducted to compare the individual fluorescence intensities of the liver, bile duct, and background fat between the 2 doses. A p value of <0.05 was considered statistically significant. All tests were performed using GraphPad Prism software version 9.4.1 (GraphPad Software, San Diego, CA). Power analysis based on results from our previous study indicated that a total of 26 patients (13 in each arm) would be required for 90% power to detect a difference in the primary outcome measure of bile duct-to-liver fluorescence intensity ratio of 0.2 between the 2 groups, given an alpha of 0.05 and a SD of 0.15. We therefore powered the study to allow for accrual of adequate numbers of subjects at each center independently.

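### The SAP's 2-way ANOVA of liver, duct and fat intensities names no patient or repeated factor, although the three readings come from one patient's recording; its secondary p values can miss 5%

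*SAP*

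**What the plan says.** The SAP is a single paragraph. After assigning Mann-Whitney tests to the quantitative and qualitative assessments, it adds: "A 2-way ANOVA was also conducted to compare the individual fluorescence intensities of the liver, bile duct, and background fat between the 2 doses". It then sets one threshold for everything: "A p value of <0.05 was considered statistically significant". It names no patient factor, repeated factor, error term or variance assumption. It also does not say whether the result of interest is the dose main effect, the dose-by-tissue interaction, or a dose contrast within each tissue. The software is named, but no model options are.

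The data structure comes from protocol section 6 (Research Plan):

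- Source of the readings: "A quantitative assessment will also be performed on the recorded visualization using ImageJ", with the ratio formed "by dividing the fluorescence intensity signal of the common bile duct by that of the surrounding fat or liver". Duct, fat and liver signals are thus read from the same patient's recording.
- Allocation: patients "will be randomized to two groups 1) low dose (0.05 mg) or 2) standard dose (2.5 mg) of ICG preoperatively". Each patient has one dose.

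The protocol does not mention the ANOVA.

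**The concern.** Each patient contributes linked readings on three tissues, and dose differs only between patients. The design therefore has two sources of error, between patients and within patients. An ordinary 2-way ANOVA has only one, a residual pooled over all readings. Two separate things can go wrong:

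- **Correlation within patients.** If a patient who is bright in one tissue tends to be bright in the others, three readings carry less information on dose than three independent ones. The pooled error is then too small for the dose main effect and, at equal SDs, too large for dose by tissue.
- **Unequal tissue SDs.** A dose contrast within one tissue needs that tissue's own variance. A pooled error is too small for the most variable tissue and too large for the least variable.

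At stake is whether the p values for individual tissue intensities can be trusted. The primary ratio has one value per patient and its own test, so it is not involved.

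**Working it through.** **The plan's own figure.** The SAP says that "a total of 26 patients (13 in each arm) would be required for 90% power" on the ratio (difference 0.2, SD 0.15, alpha 0.05). The normal formula gives 2 × (1.960 + 1.282)² × (0.15/0.2)² = 11.8, so 12 per arm. Exact two-sided t-test power is 87.7% at 12, 90.3% at 13 and 94.1% at 15 per arm. The SAP's 13 and the protocol's 15 both reproduce and are not in dispute here.

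**Inputs.** From the documents: 13 per arm (SAP) or 15 (protocol), three tissues, two doses, alpha 0.05 (taken as two-sided). Not in the documents and therefore assumed: the within-patient correlation ρ and its sign, the tissue SDs (listed as liver:duct:fat), normal data, and one reading per tissue per patient. The SD of 0.15 belongs to the ratio and does not help.

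**Dose main effect.** With tissue SDs s₁, s₂, s₃ and common correlation ρ, the true variance of the dose difference divided by the variance the pooled error assumes is

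R = 1 + 2ρ(s₁s₂ + s₁s₃ + s₂s₃)/(s₁² + s₂² + s₃²).

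The large-sample false-positive rate is 2 × [1 − Φ(1.96/√R)].

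- SDs 1:1:1: R = 1 + 2ρ. At ρ = 0.5, 1.96/√2 = 1.386, giving 16.6%.
- SDs 1:2:0.5: R = 1 + 2ρ × 3.5/5.25 = 1 + 1.333ρ. At ρ = 0.5, 1.96/√1.667 = 1.518, giving 12.9%.

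Simulation under no dose effect (40,000 trials per setting, 13 per arm, 6(n−1) = 72 residual df) agrees:

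| Dose main effect, false-positive rate | ρ = 0.1 | 0.3 | 0.5 | 0.7 |
|---|---|---|---|---|
| SDs 1:1:1 | 7.5% | 12.3% | 16.3% | 20.7% |
| SDs 1:1.5:0.75 | 7.4% | 11.2% | 15.6% | 19.4% |
| SDs 1:2:0.5 | 6.8% | 10.1% | 13.0% | 16.3% |

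At 15 per arm with equal SDs the row is 7.3/12.0/16.5/20.7%. With equal SDs at 13 per arm the rate is 5.1% at ρ = 0 and 1.2% at ρ = −0.2. With mixed signs that cancel (liver-duct −0.3, liver-fat +0.3, duct-fat 0) it is 5.0%.

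**Dose by tissue.** Simulated at ρ = 0.1/0.3/0.5/0.7: 3.7/1.5/0.4/0.02% with equal SDs, and 6.1/4.5/2.8/1.4% with SDs 1:2:0.5.

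**Per-tissue dose contrasts.** Here R is the tissue's own variance over the pooled mean variance, whatever ρ is.

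- SDs 1:1:1: R = 1 for each tissue. Simulated 4.8-5.6% at every ρ from 0 to 0.7.
- SDs 1:1.5:0.75: mean variance 3.8125/3 = 1.271, so R = 0.787, 1.770, 0.443. Simulated about 3%, 14% and 0.4%.
- SDs 1:2:0.5: mean variance 5.25/3 = 1.75, so R = 0.571, 2.286, 0.143. Simulated about 1%, 19-20% and 0%.

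**Do the alternatives work?**

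- Dose tested on the between-patient error, 2(n−1) df: 4.8-5.2% in all these settings, unequal SDs included.
- Dose by tissue on the within-patient error, 4(n−1) df: 4.8-5.1% with equal SDs but 6.5-7.2% with SDs 1:2:0.5. A Greenhouse-Geisser correction returns the latter to 4.8-5.2%.
- Separate Welch tests per tissue: 4.7-5.2% throughout.
- A patient term alone does not repair the per-tissue contrasts. Tested on the within-patient error with equal SDs, R = 1/(1−ρ), and the rates are about 6/10/16/28% at ρ = 0.1/0.3/0.5/0.7.

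**The case against.** The best case for the plan has four parts.

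1. The term 2-way ANOVA also covers a version with tissue as a repeated factor, and nothing in the SAP says the readings were treated as independent. This stands: what is shown is that the text does not specify the model, and the error rates apply only to the ordinary form.
2. The SAP speaks of individual intensities, which points to per-tissue contrasts rather than a dose effect averaged over tissues. Those contrasts are close to 5% when SDs are equal, so the missing patient factor does no harm there. This also stands, but equal SDs cannot be presumed from these documents, and the choice of contrast is itself left open.
3. Every magnitude rests on assumed correlations and SDs, and some settings show no inflation. True. Neither the size nor the direction of the error in this trial can be known from the documents. The mismatch between a single pooled error and the design does not depend on those values.
4. The analysis is additional, protocol section 10.4 describes a pilot and feasibility study, and with a 50-fold dose difference (2.5/0.05) a real intensity difference is plausible, so behaviour under no effect matters less. This limits the importance of the point. It does not remove it, because the SAP applies the same 0.05 threshold to these results.

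**Conclusion.** The concern holds. As named, the analysis does not match data with three linked readings per patient and dose varying only between patients. If the ordinary form was run, the dose main effect is declared significant too often under positive within-patient correlation: with equal SDs, about 12% at ρ = 0.3 and 21% at ρ = 0.7 against a nominal 5%. Dose by tissue is then too conservative at equal SDs. The per-tissue contrasts depend on unequal SDs instead: the most variable tissue reached about 14% to 20% and the least variable 0.4% or less under the two unequal-SD patterns tried. These figures assume normal data, one reading per tissue per patient, and correlations and SD ratios that the documents do not supply. They show what could happen, not this trial's actual error. The point concerns secondary p values only and should be corrected. Confidence is medium, because a repeated-measures version may have been run without being described.

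**What to change.** Replace the ANOVA sentence in the SAP with wording such as: *Intensities are compared with a repeated-measures 2-way ANOVA or a mixed model (patient as random effect, tissue within patient, dose between patients), with a sphericity correction or an unstructured tissue covariance. Per-tissue dose comparisons use tissue-specific variances or separate tests for each tissue, not one pooled or within-patient error.*

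The sponsor should also state which term or contrast answers its question. If tissue was already a repeated factor, it is enough to say so and to name the contrast tested and its error term.

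The cost is one or two sentences and, if the ordinary form was used, one re-run of a secondary analysis on the same data. No new data are needed, and the primary analysis and sample size do not change.

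### Does the SAP's 90% power with 26 patients fail for the Mann-Whitney test that it uses?

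*SAP*

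**What the plan says.** The SAP is a single paragraph. Its power statement says that "a total of 26 patients (13 in each arm) would be required for 90% power to detect a difference in the primary outcome measure", namely a "bile duct-to-liver fluorescence intensity ratio of 0.2 between the 2 groups", "given an alpha of 0.05 and a SD of 0.15". It does not say which test the calculation assumed or whether it was one- or two-sided. The paragraph opens by saying that "Mann-Whitney tests were conducted for the quantitative and qualitative assessments", so the primary ratio is compared by a rank test. It closes: "We therefore powered the study to allow for accrual of adequate numbers of subjects at each center independently".

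Protocol section 6 (Research Plan) uses the same difference, SD and alpha, and states: "A total of thirty patients (15 in each arm) will be required for more than a 90% power". It too names no test or sidedness.

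The title of both documents says the trial is multicenter. The protocol's body reads more like one institution's plan: section 6 says "Current standard of care for this service is to administer 2.5 mg of ICG preoperatively", and section 10.1 lists "The UF IRB assigned protocol number" among the items to be reported.

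**The concern.** A power figure should belong to the test that will be run. Here 26 is the number a two-sided t-test gives, while the SAP reports Mann-Whitney. On normal data the rank test is slightly less efficient, and at 13 per arm its exact critical value uses only 0.0441 of the 0.05 level. The stated 90% could therefore be a little generous for the primary comparison, and a reader has to guess the test and sidedness to reproduce it.

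The closing sentence of the SAP raises a second doubt. If the protocol's 30 is the total over two or more centers, at least one center has 15 or fewer patients, and the claim of adequate numbers in each center would fail.

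**Working it through.** **Inputs.** Difference 0.2, SD 0.15 and alpha 0.05 (SAP; the same in protocol section 6). Standardised difference d = 0.2/0.15 = 1.333. Two-sided testing is an assumption, supported by the SAP's non-directional description of the comparison. No dropout allowance is stated, and none is applied.

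**Step 1: reproduce the 26.** The two-sided t-test (noncentral t) needs 12.86 per arm, so 13, or 26 in total. Power is 87.7% at 12 per arm and 90.3% at 13. A one-sided t-test would need only 11 per arm (91.5%), or 22 in total, so 26 is not a one-sided t-test figure.

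**Step 2: planning formulas for Mann-Whitney, two-sided, 90% power.**
- Normal approximation 11.82 per arm, divided by the efficiency 3/π: 12.38, so 13 per arm.
- t-test size 12.86 divided by 3/π: 13.47, so 14 per arm.
- Minimum efficiency: 11.82/0.864 = 13.68, so 14 per arm.
- Noether, with P(X<Y) = 0.827: 32.7 in total, so 17 per arm.

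One standard shortcut for the test that the SAP uses therefore also gives 26.

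**Step 3: Mann-Whitney power on normal data.** Two-sided, by simulation, with exact critical values from the full null distribution (U ≤ 45, 55 and 64 at 13, 14 and 15 per arm):

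| Per arm | Total | Exact | Asymptotic, no continuity correction | t-test |
|---|---|---|---|---|
| 13 | 26 | 87.6% | 88.8% | 90.3% |
| 14 | 28 | 91.0% | 91.0% | 92.4% |
| 15 | 30 | 92.3% | 93.0% | 94.1% |

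An uneven 13 + 14 gives 89.6%, so 28 is the first total above 90%. The gap at 26 is 90 − 88.8 = 1.2 to 90 − 87.6 = 2.4 points. A one-sided Mann-Whitney test at 26 would have about 93.4%.

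**Step 4: other shapes, same SD and shift, exact two-sided test.**

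| Shape | 26 patients | 30 patients |
|---|---|---|
| Uniform | 83.5% | 89.3% |
| Logistic | 90.1% | 94.0% |
| Gamma (shape 4) | 90.7% | 94.5% |
| t, 5 df | 92.2% | 95.7% |
| Laplace | 92.4% | 95.8% |
| Lognormal (log-SD 0.5) | 94.0% | 96.9% |
| Exponential | 94.5% | 97.1% |

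**Step 5: precision of the inputs.** On normal data with 13 per arm, exact power is 89.9% for a difference of 0.208 and 90.6% for 0.21. Both round to the stated 0.2. Rounding can also work the other way, so inputs given to this precision do not separate 88% from 90%.

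**Step 6: centers.** If 30 is one center's number, the exact Mann-Whitney power there is 92.3%, and the closing sentence of the SAP holds. If 30 is the total over two or more centers, a center with 15 patients has 59.7% (7 vs 8) or 61.9% (6 vs 9) by exact Mann-Whitney, and 66.4% or 64.8% by t-test. The sentence would then not hold.

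**The case for a change.** The strongest case for a change is that the power statement concerns the primary outcome, cannot be reproduced without guessing, and is slightly too high on normal data for the test actually used. Two or three sentences would settle it and would cost nothing in accrual or analysis. The omission is real, and the normal-model figures stand.

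The step from omission to error does not. The 26 is correct for a t-test and for one accepted rank-test shortcut. The 88% needs a normality assumption that the SAP does not make and that a rank test does not need. Writing 88% and 92% into the SAP would replace an unattributed figure with one that rests on an assumption the investigators never stated.

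The point about centers is the more consequential one if the unfavourable reading is right, since power of about 60% is not adequate. But the documents do not establish that reading. A protocol written around one institution fits 30 as that site's own number, and the SAP's last sentence can be read as saying that 26 suffices within a single center. That the basis of the number is unstated remains true; that the trial is underpowered by center is not shown.

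**Conclusion.** The concern does not call for a change. What is missing is descriptive: the test and sidedness behind the 26, and whether the number is per center or overall. A two-sided t-test is recoverable as a sufficient source for the 26, and two-sided testing is the natural reading of the SAP.

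For the Mann-Whitney test, the possible overstatement at 26 is 1.2 to 2.4 points on normal data. It is larger for a flat distribution (83.5%) and absent for the six skewed or heavier-tailed shapes tried. At the protocol's 30 patients, power is about 92% under normality, in line with that document's own claim of more than 90%; of the shapes tried, only the uniform falls just short there (89.3%). Protocol section 10.4 also describes a pilot and feasibility study that does not target a primary efficacy difference, so a point or two of planned power carries little weight. The SAP reports the tests as already carried out, so restating the power would alter neither accrual nor the primary comparison.

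This conclusion assumes equal SDs in the two arms, two-sided testing, and 30 as the working number. If 30 proved to be a total shared between centers, the SAP's closing sentence would be overstated, but the power of the overall comparison would be unaffected.
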